23.1 Scope of Analysis

This addendum integrates the analysis plan described in protocol Section 8. The analysis presented in this Addendum, will be applied to data from all patients enrolled in the study and suitable to be implanted with the Tendyne 1.0 valve and Tendyne LP valve in Europe and worldwide.

23.2 Purpose

The data gathered in this study will be used to support conformity requirements for CE Mark of the Tendyne Mitral Valve using an appropriately powered sample size as described in Section 1 to enable assessment of the 30-day safety and performance endpoints of the Tendyne Mitral Valve System in the intended populations.

This study will be continued after the CE Mark to include a maximum of 350 patients enrolled at a maximum of 40 clinical sites with the purpose to collect broader safety and performance data as part of the Tendyne post-market follow-up program. [REDACTED]

[REDACTED]

[REDACTED]

[REDACTED]

[REDACTED]

All statistical analyses will be performed using Statistical Analysis System (SAS) for Windows (version 9.4, SAS Institute Inc. Cary, NC) or other widely accepted statistical or graphical software.

23.3 Hypotheses (H0, HA) for 30-day mortality

[REDACTED]

[REDACTED]

[REDACTED]

[REDACTED]

[REDACTED]

[REDACTED]

[REDACTED]

23.4 Calculation of Sample Size for Mortality

[REDACTED]

[REDACTED]	[REDACTED]	[REDACTED]
[REDACTED]	[REDACTED]	[REDACTED]
[REDACTED]	[REDACTED]	[REDACTED]
[REDACTED]	[REDACTED]	[REDACTED]

[REDACTED]

23.5 Criteria for Termination

[REDACTED]

Additionally, the independent Data Safety Monitoring Board (DSMB) will be monitoring the conduct of the trial. The protocol Section 21.1 states that the entire study or any individual site may be suspended or terminated prematurely by the sponsor based on recommendation from the DSMB or if otherwise deemed necessary. Possible reasons for early study termination include the discovery of an unexpected, significant, or unacceptable risk to the subjects enrolled in the study. For details, refer to protocol Section 19.6.

The role of the DSMB is described in the protocol Section 19.6. The DSMB is responsible for the study review and to recommend any modification or study termination for any perceived safety concern based on clinical judgement, including but not limited to: a higher than anticipated rate for any component of the primary safety endpoint; device failures resulting in adverse events; or unexpected SAEs. Possible reasons for early study termination include the discovery of an unexpected, significant, or unacceptable risk to the subjects enrolled in the study.

At the conclusion of each DSMB meeting, a recommendation will be made to the sponsor on whether to continue, suspend, modify or stop the study.

#### 1. SYNOPSIS OF STUDY DESIGN AND PROCEDURES

## 1.1 Purpose of the Statistical Analysis Plan

This statistical analysis plan (SAP) is intended to provide a detailed and comprehensive description of the planned methodology and analysis to be used to support conformity requirements for CE Mark of the Tendyne Mitral Valve System with data from the Tendyne CS-03 clinical investigation.

## 1.2 Study Objective

The objective of the trial is to evaluate the safety and performance of Tendyne Mitral Valve System in the treatment of severe mitral regurgitation in subjects with symptomatic, severe mitral valve regurgitation, who are not suitable for surgical treatment and in whom existing co-morbidities would not preclude the expected benefit from reduction of the mitral regurgitation.

### 1.3 Study Design

This is a prospective, single-arm, multicenter study designed to evaluate the Tendyne Mitral Valve System in patients with significant mitral regurgitation.

This study is designed in accordance with the Mitral Valve Academic Research Consortium (MVARC) 2015 guidelines and the ISO 5840-3:2013 standard. The study is conducted under ISO 14155-2011 standard.

The data gathered in this study will be used to support conformity requirements for CE Mark of the Tendyne Mitral Valve System and to evaluate long-term safety and performance of Tendyne Mitral Valve in the intended population.

All enrolled subjects will be followed at 30 days, 90 days, 6 months, 12 months, and annually thereafter through 5 years from the index procedure.

A clinical investigation report will be prepared for CE Mark based on clinical data from at least 86 subjects who have completed or crossed the 12-month follow-up.

The study will continue to enroll after the CE Mark and collect long-term safety and performance data as part of the Tendyne post-market follow-up program.

CONFIDENTIAL Page 3 of 15

## 1.3.1 Primary Endpoints

## 1.3.1.1 Primary Safety Endpoint

The primary safety endpoint is a composite of device success (as defined in **Section 1.3.2.2**) and freedom from the following device- or procedure-related serious adverse events (SAEs) at 30 days post the index procedure, per adjudication by the Clinical Events Committee (CEC):

- Cardiovascular death
- Reintervention caused by valve-related dysfunction
- Disabling stroke
- Myocardial infarction (MI)
- Life-threatening bleeding (BARC Type 2, 3, and 5)
- Major Vascular Complications
- Renal failure requiring dialysis
- Other device-related SAEs: device migration, embolization, fracture, hemolysis, thrombosis or endocarditis
- Other procedure-related SAEs: cardiac tamponade, sepsis

Stroke and MI classifications will be per the Valve Academic Research Consortium – 2 (VARC-2). Life-threatening bleeding classifications will be per the Bleeding Academic Research Consortium (BARC) consensus.

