7.1.2 Device Success Definition (at 30 day and all post-procedural time points)

Alive with the following:

- Disabling stroke free, with
- Original intended device in place, and
- No additional surgical or interventional procedures related to access or the device, and
- Intended performance of the device:
 - No Device specific adverse events, such as migration, embolization, fracture, hemolysis, thrombosis or endocarditis, and
 - Maintenance of expected hemodynamic performance (e.g., central mitral regurgitation (MR) < 1+; mitral valve gradient < 6 mmHg or effective orifice area (EOA) > 1.5 cm²) and,
 - No para-device complications (left ventricular outflow tract (LVOT) obstruction: >20 mmHg increase in LVOT gradient vs. baseline; paravalvular leak (PVL) > 1+; effects on coronary circulation or other heart structures, e.g., erosion or need for permanent pacemaker implantation.

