7.3.2 Primary Safety Endpoints

Device success and freedom from the following device- or procedure-related serious adverse events (SAEs) at 30 days post implant, as classified by the Clinical Events Committee:

- Cardiovascular death
- Reintervention caused by valve-related dysfunction
- Disabling Stroke
- Myocardial infarction (MI)
- Life-threatening bleeding (BARC Type 2, 3, and 5)
- Major Vascular Complications
- Renal failure requiring dialysis
- Other device-related SAEs
- Other procedure-related SAEs

Stroke and MI classifications will be per the VARC-2. Life-threatening bleeding classifications will be per the Bleeding Academic Research Consortium (BARC) consensus. Criteria are provided in Appendix A.

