7.3.4 Secondary Safety Endpoints

Through two years post implant:

- Device success, and
- No device or procedure related SAEs

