21.2 Routine Closeout

At the end of the study, routine closeout activities will be conducted to ensure site records are complete, study data are complete and accurate, remaining study materials and investigational devices are returned to the sponsor, arrangements are made for record retention, and institutional review boards/ethics committees are notified.

22 Appendix A

Normative References

- ISO 14155 ISO 14155:2011(E). Clinical investigation of medical devices for human subjects — Good clinical practice.
- ISO 5840-3 ISO 5840-3:2013(E). Cardiovascular implants — Cardiac valve prostheses — Part 3: Heart valve substitutes implanted by transcatheter techniques.
-

Adverse Device Effect (from ISO 14155)

Adverse event related to the use of an investigational medical device.

Adverse Event

Events that fall under the definition of Adverse Event from either ISO 14155 or ISO 5840-3: (from ISO 14155) Any untoward medical occurrence, unintended disease or injury, or untoward clinical signs (including abnormal laboratory findings) in subjects, users or other persons, whether or not related to the investigational medical device.

Note 1 This definition includes events related to the investigational medical device or the comparator.

Note 2 This definition includes events related to the procedures involved.

Note 3 For users or other persons, this definition is restricted to events related to investigational medical devices.

(from ISO 5840-3) Untoward medical occurrence in a study subject, which does not necessarily have to have a causal relationship with study treatment.

Bleeding (from BARC)

Six types are hierarchically defined from type 0 in which there is no bleeding to type 5 with fatal bleeding. Type 1 is in which the patient does not seek treatment. Type 2 is in which intervention or admission to hospital occurs. Type 3a is overt bleeding plus hemoglobin drop of 3 to less than 5 g/dl or transfusion. Type 3b is overt bleeding plus hemoglobin drop of at least 5 g/dl, cardiac tamponade, bleeding requiring surgical intervention or intravenous vasoactive agents. Type 3c is intracranial hemorrhage or intraocular bleeding compromising vision. Type 4 is coronary artery bypass grafting-related bleeding and type 5 is fatal bleeding.

Body Surface Area (from ISO 5840-3)

Total surface area (m²) of the human body. NOTE: This can be calculated (Mosteller's formula) as the square root of product of the weight in kg times the height in cm divided by 3600.

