#### 1.3.4 Additional Endpoints

Additional study endpoints include the following:

- Length of hospital stay
- All-cause mortality at 3 months
- A composite endpoint of device success and freedom from device- or SAEs at 2 years post
  the index procedure. This endpoint is defined similarly as the primary safety endpoint in
  Section 1.3.1.1, except that the endpoint will be measured at 2 years post the index
  procedure.

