#### 2.2 Study Endpoint Analyses

## 2.2.1 Primary Safety Endpoint Analyses

The primary analysis will be based on the TP population. The composite endpoint will be summarized as the proportion of subjects with device success (definition in **Section 1.3.2.2**) and freedom from device- or procedure-related SAEs at 30 days post the index procedure, per CEC adjudication, along with the 95% exact confidence interval. Each component of the primary composite endpoint will also be summarized separately using descriptive statistics.

Similar analyses will be provided for the IPP population.

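### SAP 1.3.1.1 attaches named lists to the protocol's two open-ended related-SAE components, so the 30-day safety result can only stay the same or look better

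*SAP*

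**What the plan says.** Protocol 7.3.2, like the synopsis, defines the 30-day primary safety endpoint as device success plus freedom from nine kinds of device- or procedure-related SAE, as classified by the CEC. The last two kinds are catch-alls. The procedure one reads simply "Other procedure-related SAEs", and its device counterpart is equally unrestricted.

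SAP 1.3.1.1 keeps the same nine components but adds a colon and named events to these two: "Other device-related SAEs: device migration, embolization, fracture, hemolysis, thrombosis or endocarditis" and "Other procedure-related SAEs: cardiac tamponade, sepsis".

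SAP 2.2.1, which says what will be computed, drops the lists and speaks of "freedom from device- or procedure-related SAEs at 30 days post the index procedure, per CEC adjudication".

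The two-year composite in SAP 1.3.4 refers back to 1.3.1.1: "This endpoint is defined similarly as the primary safety endpoint in" that section. The protocol's two-year counterpart (7.3.4) requires device success and "No device or procedure related SAEs".

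**The concern.** A catch-all component exists to count related SAEs that no specific component names. If it is limited to two procedure events and six device events, related SAEs outside those lists fall out of the primary safety endpoint, although the protocol counts them. Two analysts, one working from SAP 1.3.1.1 and the other from SAP 2.2.1, could report different primary safety proportions from the same data.

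This is a single-arm CE-mark study whose endpoints were chosen so that its estimates can be compared with those of other studies (protocol Section 7). With no control arm, the estimate itself is the safety result. Reporting each component separately, as SAP 2.2.1 plans, does not repair the gap, because an unlisted related SAE belongs to no component. Protocol 23.5 also has the DSMB consider the rate of any primary safety component, so the component definitions matter for monitoring too.

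**Working it through.** The readable text gives no expected rate or performance goal for this endpoint, so there is no stated figure to reproduce. The check has three parts: the wording, the direction of the effect, and an illustration of size.

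**1. Wording side by side**

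| Place | Other device-related SAEs | Other procedure-related SAEs |
|---|---|---|
| Protocol synopsis and 7.3.2 | unrestricted | unrestricted |
| SAP 1.3.1.1 | six named events | tamponade, sepsis |
| SAP 2.2.1 | no list | no list |

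The SAP lists carry no *such as* or *including*. The protocol does use such a phrase before the same six device events in its device-success definition (7.1.2): "No Device specific adverse events, such as migration, embolization, fracture, hemolysis, thrombosis or endocarditis".

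**2. Which events drop out**

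An event drops out if it is a related SAE, is on neither list, triggers none of the other seven components, and does not cause device-success failure. On the procedure side:

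- Three cases follow from the definitions: non-disabling stroke or TIA (only disabling stroke is named, both here and in device success), renal failure without dialysis, and serious infection short of sepsis.
- Respiratory failure, new or worsening heart failure, arrhythmia without a pacemaker, and pulmonary embolism have no component of their own.

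All are types of event anticipated in protocol 18.2. Each is serious if, for example, it prolongs hospitalization (Appendix A).

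The procedure list adds little beyond sepsis, because the BARC text in Appendix A already covers tamponade: "Type 3b is overt bleeding plus hemoglobin drop of at least 5 g/dl, cardiac tamponade". The device list repeats the protocol's device-success examples. The SAP's own device-success sub-list is not in the public text, so that overlap cannot be checked on the SAP side.

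**3. Direction**

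For subject *i*, let each indicator be 1 or 0:

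- D = device success
- N = none of the seven specific components
- L = no listed other event
- U = no unlisted other related SAE

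Success under the SAP lists is D·N·L. Success under the protocol is D·N·L·U. Since U ≤ 1, protocol success never exceeds SAP success for any subject. Summed over *n* subjects:

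p(SAP) − p(protocol) = k/n ≥ 0,

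where *k* is the number of subjects whose only failure is an unlisted related SAE. This holds D and the population the same in both definitions.

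**4. Size, as illustration only**

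Take n = 86, the SAP 1.3 minimum for the 12-month report; this is not the 30-day treated population. The starting counts (60 and 73 successes under the lists) and the values of *k* are assumptions. Intervals are exact (Clopper-Pearson) 95%: lower limit = the 0.025 quantile of Beta(x, n−x+1), upper limit = the 0.975 quantile of Beta(x+1, n−x).

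| k (share of 86) | From 60/86 under the lists | From 73/86 under the lists |
|---|---|---|
| 0 (0%) | 60/86 = 69.8% (58.9–79.2) | 73/86 = 84.9% (75.5–91.7) |
| 4 (4.7%) | 56/86 = 65.1% (54.1–75.1) | 69/86 = 80.2% (70.2–88.0) |
| 8 (9.3%) | 52/86 = 60.5% (49.3–70.8) | 65/86 = 75.6% (65.1–84.2) |
| 17 (19.8%) | 43/86 = 50.0% (39.0–61.0) | 56/86 = 65.1% (54.1–75.1) |

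The protocol-defined estimate falls below the lower limit of the list-based interval at k = 10 from 60/86 (50/86 = 58.1%, below 58.9%) and at k = 9 from 73/86 (64/86 = 74.4%, below 75.5%).

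**The case against.** **The lists may be examples.** SAP 2.2.1 has no list, 1.3.1.1 keeps the word *other* before each colon, and the six device events match a protocol passage that treats them as examples. That reading is possible, but the SAP does not state it. On either reading the text needs changing: to say the lists are examples, or to remove a departure from the protocol.

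**The protocol may not commit to one composite.** Protocol 8.5.2 evaluates each component and makes composites optional; its data-analysis text is blacked out. This does not help, because the two individual *other* components are narrowed as well.

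**The protocol sets its own thresholds.** If the catch-all takes in non-disabling stroke and renal failure without dialysis, the disabling and dialysis thresholds do no work in the composite. It is fair to ask what was intended for those two cases. But protocol 7.3.4 and SAP 2.2.1 both refer to related SAEs without a threshold, and respiratory failure, arrhythmia and non-septic infection do not depend on this question.

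**The affected set is limited.** BARC type 2 bleeding, pacemaker need, and additional procedures related to access or the device still fail a subject by another route, and the device list is largely redundant with device success. This stands: the effect lies mainly in the procedure component.

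**No visible decision turns on it.** SAP 2.2.1 shows an estimate with an interval and no hypothesis, and the two-year composite is descriptive. This also stands. The harm is to the reported estimate and its comparison with other studies, not to a visible pass/fail test.

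**Conclusion.** The concern holds: SAP 1.3.1.1 is wrong as written. It narrows two components that the protocol leaves open, and it conflicts with SAP 2.2.1. For this wording change, with device success and population held fixed, the list-based success proportion is equal to or higher than the protocol-defined one. The difference is exactly the share of subjects whose only failure is an unlisted related SAE. That share cannot be found from the documents and may be zero; the percentages above rest wholly on assumed counts. The two-year composite inherits the same narrowing through its reference to 1.3.1.1. Because this is the primary safety endpoint, the text should be corrected before the result is reported.

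**What to change.** - In SAP 1.3.1.1, state that every other CEC-adjudicated device-related SAE and every other CEC-adjudicated procedure-related SAE through day 30 counts. Show the named events as examples or as a breakdown by type.
- Use the same wording in SAP 2.2.1 and carry it into the two-year composite in SAP 1.3.4, so that it agrees with protocol 7.3.4.
- If a narrower composite is wanted, report it only as a labelled supportive endpoint.

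The cost is SAP wording in three places. No new data are needed, because the CEC already classifies all SAEs (protocol 19.5) and related events (SAP 1.5). The only downside is that the stated safety figure may be somewhat less favourable.

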#### 1.3.1.2 Primary Performance Endpoint

The primary performance endpoint is the proportion of subjects with mitral regurgitation (MR) grade ≤ 2, per echocardiography core laboratory, at 30 days post the index procedure. If the 30-day echocardiography data is not available, the data from the next closest visit will be used.

## 1.3.2 Secondary Endpoints

The secondary endpoints are:

- All-cause mortality at 30 days
- Change from baseline in distance walked on the 6MWT at 6 months and 12 months
- Change from baseline in QoL, as measured by KCCQ at 6 months and 12 months
- Change in proportion of NYHA Functional Classification I or II at 12 months

CONFIDENTIAL Page 4 of 15

## 1.3.3 Performance Endpoints

#### 1.3.3.1 Technical Success

Technical success is a composite endpoint measured at exit from the procedure room, defined as subject is alive with the following:

- Successful access, delivery and retrieval of the transcatheter valve delivery system, and
- Deployment and correct positioning of the correctly sized valve, and
- No need for additional emergency surgery or re-intervention related to the device or access procedure.

#### 1.3.3.2 Device Success

Device success is a composite endpoint measured at 30 days post the index procedure and all post-procedural time points, defined as subject is alive with the following:

- Disabling stroke free, and
- Original intended device in place, and
- · No additional surgical or interventional procedures related to access or the device, and
- Intended performance of the device:

#### 1.3.3.3 Individual Patient Success

Individual patient success is a composite endpoint measured at 1 year post the index procedure, defined as device success (**Section 1.3.2.2**) and all of the following:

- No re-hospitalizations or re-interventions for heart failure
- Improvement in New York Heart Association (NYHA) functional class (≥ 1 compared to baseline)

CONFIDENTIAL Page 5 of 15

- Improvement in distance walked, 6 Minute Walk Test (6MWT) (≥ 50 meters compared to baseline)
- Improvement in Kansas City Cardiomyopathy Questionnaire scores (KCCQ) (≥ 10 compared to baseline)

#### 1.3.4 Additional Endpoints

Additional study endpoints include the following:

- Length of hospital stay
- All-cause mortality at 3 months
- A composite endpoint of device success and freedom from device- or SAEs at 2 years post
  the index procedure. This endpoint is defined similarly as the primary safety endpoint in
  Section 1.3.1.1, except that the endpoint will be measured at 2 years post the index
  procedure.

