7.3.3 Secondary Safety Objective

To evaluate long-term safety of the Tendyne Bioprosthetic Mitral Valve System.

Follow-up for secondary endpoints will be continued for 2 years. Additional follow-up will be obtained for up to 5 years as recommended by most recent guidelines, to capture long-term

data on less common or unanticipated adverse events, on adverse events which are time-related (e.g., structural deterioration, adverse effects on native valve anatomy) and on long-term performance.

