7.5 Additional Endpoints

- Length of ICU stay
- Length of hospital stay
- 30 day mortality
- 3-month mortality

8 Analysis Plan and Sample Size Justification

[REDACTED]

[REDACTED]

[REDACTED]

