8.5.3 Valve System Usability Objective

The valve system usability objective is to evaluate information on the usability of the Tendyne Bioprosthetic Mitral Valve System.

Data included in the analysis: All usability data gathered from implanters will be analyzed. Data will be implanters' assessments of usability, especially as it relates to the ability to successfully deliver, position, and deploy the Tendyne Mitral Valve in the desired anatomical location. Data will also include information on retrievability, if available.

Data Analysis: [REDACTED]

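### Below the primary level the protocol and SAP rank endpoints differently, and the SAP narrows the protocol's two-year secondary safety endpoint

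*SAP*

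**What the plan says.** **Protocol.** Section 7.3.4, headed Secondary Safety Endpoints, has one entry with two parts: device success, and "No device or procedure related SAEs". Its time frame is "Through two years post implant", and the synopsis agrees. Section 7.3.3 ties follow-up to it: "Follow-up for secondary endpoints will be continued for 2 years". Section 7.5 lists four additional endpoints: "Length of ICU stay", hospital stay, and mortality at 30 days and at 3 months. Appendix B nevertheless has a section titled "Hypotheses (H0, HA) for 30-day mortality" and another on sample size for mortality; the content of both is redacted. NYHA class, six-minute walk and KCCQ enter section 7 only as one-year improvement thresholds inside Individual Patient Success (7.2).

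**SAP.** Section 1.3.2 lists four secondary endpoints: 30-day all-cause mortality, change in walk distance at 6 and 12 months, change in KCCQ at 6 and 12 months, and "Change in proportion of NYHA Functional Classification I or II at 12 months". The two-year composite is in section 1.3.4, Additional Endpoints: "A composite endpoint of device success and freedom from device- or SAEs at 2 years". The next sentence there says that it follows the definition in 1.3.1.1 apart from the time point. In 1.3.1.1 the 'other' device-related SAEs are spelled out as migration, embolization, fracture, hemolysis, thrombosis or endocarditis, and the 'other' procedure-related SAEs as tamponade and sepsis. Hospital stay and 3-month mortality complete the list in 1.3.4.

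**The concern.** In a single-arm study meant to support CE marking, a reader needs to know which results were specified in advance and at what level. Here the two documents answer differently for everything ranked below primary.

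The more serious part is content. The two-year safety result is the protocol's only endpoint labelled secondary, and the SAP changes which events count as failures. Followed as written, the SAP would report a narrower safety result than the one the protocol promises. The SAP would also formally test an NYHA Class I/II proportion that Protocol section 7 does not list.

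**Working it through.** No alpha, power or sample-size figure is involved. The check is a comparison of the readable lists, followed by the logic of the two-year definition.

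**1. Levels side by side**

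| Item | Protocol | SAP |
|---|---|---|
| Two-year safety composite | Secondary (7.3.4) | Additional (1.3.4) |
| 30-day mortality | Additional (7.5); hypothesis and sample-size sections in Appendix B | Secondary (1.3.2) |
| Walk distance change, 6 and 12 months | Not listed; 1-year gain of at least 50 m is a component in 7.2 | Secondary (1.3.2) |
| KCCQ change, 6 and 12 months | Not listed; 1-year gain of at least 10 is a component in 7.2 | Secondary (1.3.2) |
| NYHA I/II proportion, 12 months | Not listed; 1-year gain of at least one class is a component in 7.2 | Secondary (1.3.2), one-sided 5% McNemar test (2.2.4.4) |
| Hospital stay | Additional (7.5) | Additional (1.3.4) |
| 3-month mortality | Additional (7.5) | Additional (1.3.4) |
| ICU stay | Additional (7.5) | Not named in readable text |

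Counts:
- The one endpoint that section 7 labels secondary is additional in the SAP (1 of 1).
- None of the SAP's four secondary endpoints (1 + 2 + 2 + 1 = 6 endpoint-by-time results) is labelled secondary in section 7.
- Of the protocol's four additional endpoints, two keep that level, one is raised and one is absent.

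**2. Two-year composite: which SAEs count**

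Let A be the patients with any device- or procedure-related SAE (protocol), and B those with a related SAE in one of the categories in SAP 1.3.1.1. Every patient in B is also in A. With the same data and time window, SAP success is therefore at least as high as protocol success. The gap is

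(patients whose only failure is an unlisted related SAE) / N.

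Such events are plausible. Protocol 18.2 anticipates respiratory failure, liver failure and esophageal perforation. If serious and judged procedure-related, each fails the protocol endpoint, but none is on the SAP list.

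The documents give no rate for unlisted related SAEs, so the gap cannot be estimated. As an illustration only, each such patient moves the proportion by 1/86 = 1.16 percentage points if N is 86 (the SAP's minimum number past 12 months for the CE Mark report), or by 1/350 = 0.29 points if N is 350 (the protocol's enrollment maximum). Neither is stated to be the two-year denominator.

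**3. Two-year composite: time window**

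The protocol covers the whole period; the SAP wording fixes a time point. Device success is assessed at every post-procedural time point. A patient who fails on a gradient at six months and meets the limit at two years fails over the period, but could be counted a success at two years. The SAP does not say which reading applies.

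**4. NYHA: a different quantity**

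The protocol component is improvement by at least one class, and Class II patients are eligible (6.4.1). A move from II to I, or from IV to III, meets the protocol component but leaves the SAP's Class I/II proportion unchanged. The McNemar test is thus not a restatement of the protocol component.

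**The case against.** Several stronger readings are tempting, and the documents do not support them.

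- **That listing the two-year endpoint as additional reduces it to a merely descriptive result.** Descriptive reporting is not a lower tier in this SAP. Primary safety is itself only a proportion with an exact 95% interval (2.2.1). Section 2.2.5 sends additional endpoints to section 2.1, which gives categorical variables the same interval. No readable protocol text attaches a test to the two-year endpoint either.
- **That the mortality test lacks protocol support.** Appendix B supplements the protocol's section 8 and has hypothesis and sample-size sections for 30-day mortality. What remains is a labelling conflict between 7.5, Appendix B and the SAP.
- **That usability would go unreported.** Protocol 8.5.3 already commits: "All usability data gathered from implanters will be analyzed". SAP silence does not cancel that, and the readable SAP skips section 2.3.
- **That all the functional endpoints are formally tested.** Only NYHA has a readable test. For KCCQ and walk distance the readable text says only that follow-up values will be compared with baseline.
- **That the broken phrase in SAP 1.3.4 leaves the endpoint undefined.** The cross-reference to 1.3.1.1 supplies procedure-related. It also imports the restricted SAE list.

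Two further points deserve weight. Protocol 7.3.4 is headed as a list of safety endpoints, and Protocol 8.6, on evaluating secondary endpoints, is redacted and could name others. The SAP's CE Mark purpose, with its 12-month data cut, would also fit a lower rank for a two-year endpoint, although the SAP does not give that reason and states long-term safety as an aim (1.3).

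These points remove the stronger claims. They do not remove the differences in label, SAE scope and time window.

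**Conclusion.** The readable lists conflict below the primary level, and for two-year safety the conflict goes beyond the label. The SAP version counts fewer kinds of SAE and is worded for a time point, not a period. On SAE scope alone it can only match or exceed the protocol's success proportion. By how much is unknown.

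This rests on reading the events named in SAP 1.3.1.1 as a closed list, as they are written. If they were meant as examples, the scope difference disappears and the label and time-window differences remain.

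The other mismatches are of level and listing. 30-day mortality needs one level, the functional analyses need a place in the protocol or an exploratory label, and ICU stay is missing from the readable SAP. No error rate or sample size is shown to change. All of this is limited to unredacted text. The documents should be reconciled before two-year results are analyzed.

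**What to change.** 1. Put the protocol's endpoint into SAP 1.3.2: device success and no device- or procedure-related SAE of any kind, over the full two years. Report it as a proportion with an exact 95% confidence interval, and remove the version in SAP 1.3.4.
2. Give 30-day mortality one level and use it in Protocol 7.5, Appendix B and the SAP.
3. List the walk-distance, KCCQ and NYHA I/II analyses as secondary in Protocol section 7, or label them exploratory in the SAP.
4. Add ICU stay to SAP 1.3.4.

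The cost is wording in both documents and one short descriptive table for ICU stay. The wider SAE scope needs no new collection, because all adverse events are recorded through study exit and the CEC classifies all serious ones.
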